1.3.8 Laboratory and other investigations

Examinations will be performed prior to the surgical abortion that are in accordance with the standard of care. No additional laboratory studies will be performed for the clinical trial.

1.3.9 Data management

Prior to study initiation, a database will be developed using a web-based password-protected relational database (REDCap). All data will be collected electronically into the database on tablets. All consent documents will be filed in a locked cabinet and stored for future reference. Data will be collected on research-designated tablets.

1.3.10 Data analysis

We will compare groups on the primary continuous outcome measure (pain score on 100-mm point VAS) using T-tests and Mann-Whitney U test. Chi-square and T-tests will be used to evaluate secondary outcomes for categorical and continuous variables, respectively. Baseline characteristics will be evaluated for potential interaction or confounding with primary and secondary outcomes.

All available data from completed questions will be used for analysis, including partially completed surveys. Participants may request that their data not be used for analysis if a request is received prior to analysis as mentioned in the consent form. A statistician will be consulted to assist with the analysis as needed.

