1.1.2 Objectives and hypotheses

Pain control during and after abortion is a family planning research priority, as identified by the Society for Family Planning [10]. Pain management regimens for surgical abortion may include: local anesthetic, oral analgesics, moderate sedation, deep sedation, or a combination of approaches. While several recent studies have evaluated supplemental medications or therapies intended to reduce abortion-related pain, such as non-steroidal anti-inflammatory drugs (NSAIDs), narcotics, anxiolytics, misoprostol, nitrous oxide, or music, most have failed to note improved pain scores. Optimal pain management has yet to be established as many women continue to report moderate to severe pain during and after an abortion procedure [11].

We hypothesize that adding gabapentin pre-operatively to local anesthesia will reduce perioperative pain associated with surgical abortion. Additionally, we hypothesize that pre-operative gabapentin will reduce perioperative nausea, vomiting, and anxiety, as well as reduce post-operative pain and consumption of pain medication with few adverse effects.

Primary Aim: To evaluate the impact of adjunctive pre-operative gabapentin on intraoperative pain scores (at time of evacuation with the start of suction) during surgical abortion.

Secondary Aims:

- To evaluate the impact of pre-operative gabapentin on pain scores post operatively (removal of speculum, 10 and 30 minutes after procedure, at time of discharge and 24 hours after procedure)
- To evaluate the impact of pre-operative gabapentin on:
 - Perioperative nausea and vomiting
 - Perioperative anxiety
- To evaluate the impact of pre-operative gabapentin on perioperative medication consumption, and pain medication consumption up to 24 hours after the procedure
- To evaluate safety of gabapentin in this setting (monitor side effects or adverse events of gabapentin in this setting)

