1.3 Design and Methodology

1.3.1 Research design and General Methodology Approach

This is a randomized double-blind placebo-controlled trial evaluating the impact of gabapentin given preoperatively on perioperative pain scores for women receiving a surgical abortion. Randomization will be done using computer generated random Fellowship in Family Planning Research Proposal Outline

numbers. Allocation concealment will be maintained by identically labeled sealed sequentially numbered pill containers. Gabapentin and placebo will be packaged in identical gelatin capsules and sealed by an independent pharmacy. Gabapentin and placebo gelatin capsules will be indistinguishable by appearance, thus maintaining double blinding.

Primary study outcomes: Our primary outcome measure will be pain score using a 100-mm visual analog scale (VAS) measured intraoperatively at time of evacuation.

Secondary outcomes: We will also be measuring pain on the 100-mm VAS preoperatively immediately prior to the procedure, at completion of the procedure (removal of the speculum), 10 minutes and 30 minutes following the procedure, and at discharge. Nausea and vomiting will be assessed during the same time intervals using a 100-mm VAS scale. Anxiety prior to the procedure will be measured using the preoperative state trait anxiety inventory. Side effects will be assessed using a checklist prior to discharge. We will also be contacting participants on post-operative day 1 to assess pain, nausea, vomiting, side effects and general satisfaction with the procedure (on a 5-point scale). The quantity and type of medications used perioperatively and post-operatively, including medications used at home in the 24 hours post-operatively, will be abstracted from the clinical record and assessed on the phone. Outcome measures will be collected on a tablet using a web-based password-protected relational database (REDCap). All VAS scale scoring and questionnaires will be completed using this database on a research-designated tablet.

Baseline Characteristics and Covariates:

We will collect baseline demographics, medical history (gravidity, parity, prior abortions (medical and surgical), gestational age, drug and alcohol use, psychiatric or sexual assault history, medications used at home and given at the clinic preoperatively, and indication for procedure (personal/social, fetal, or maternal health). This information will also be obtained using a research-designated tablet.

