an 80% power, using a p-value of 0.05, to detect a 15-mm difference on a 100-mm VAS among women presenting for abortion. The enrollment of 96 women is estimated based on a sample size for a t-test. This sample size is adjusted based on the ARE (asymptotic relative efficiency) of the Mann-Whitney U test statistic. The ARE is based on distribution, which is unknown here. Since the ARE for the Mann-Whitney is never less than 0.864, the sample size from the t-test above will be divided by this value. This creates a sample size of 111 women. To account for a potential 20% loss to follow up, the target enrollment goal will be increased to 133 total women for participation in this study.

Inclusion and Exclusion Criteria:

Inclusion criteria include:

- Women ≥ 18 years-old
- Presenting for a surgical abortion
- Fluency in English and able to provide informed consent
- Has a driver to take them home

Exclusion criteria include:

- Allergy, sensitivity or contraindication to gabapentin
- Severe renal disease
- Currently using gabapentin or pregabalin
- Contraindication to outpatient abortion under local anesthesia

Although patients on any chronic pain medications or with pre-existing pain conditions or history of alcohol or drug use may have a different metabolism or effect of the drugs, these women will not be excluded. Rather, data will be collected on these factors to evaluate the impact of these factors on study outcomes.

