The abortion providers are not involved in the discussion with the patient regarding “timing, method, or procedures used to terminate a pregnancy”. This is a discussion that the clinic staff has with the patient after ultrasound evaluation (to confirm gestational age) and financial counseling. The patient also goes through options counseling with clinic staff (not the abortion provider) during which the different types of procedures are discussed (medical vs surgical procedure based on gestational age). The study team will only begin interaction with the potential subject/patient once they’ve selected local anesthesia and paid for their procedure. The Investigators will only be involved after this point. Investigator involvement may include consenting the subject, administering the study drug, performing the procedure, and other study related activities such as administering the questionnaire. There is one abortion provider per day at Atlanta Women’s Clinic and if an investigator is the provider for that day, she will not participate in any other study-related activities.

The person obtaining the consent will be a member of the study team. This person will have no prior contact with the study patient. This person will not be scheduling the appointment, discussing options counseling, advising about the procedural options, or performing ultrasound or other laboratory work-up for the participant prior to the procedure. There is a clear separation between study staff and clinic staff prior to the enrollment of participants into the study,

Randomization, Allocation Method and Blinding:

Women who enroll and meet study inclusion criteria will be eligible for participation. *Randomization* will be done using computer-generated random numbers (randomization.com) in variable blocks of 4 and 6. *Allocation* concealment will be maintained by identically labeled sealed sequentially numbered opaque pill containers. Gabapentin and placebo tablets will be indistinguishable by appearance (both gelatin capsules), thus maintaining blinding for participants and assessors. To maintain double *blinding* for both investigators and participants, an individual not associated with study conduct will create the randomization sequence and allocation containers. The study drug

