1.3.11 Number of subjects and statistical power

We will enroll a total of 133 women. This number was determined to give us sufficient power to detect a **15-mm difference on the 100-mm VAS**. A 100-mm pain visual analog scale has been shown to be useful for the evaluation of pain in prior pain abortion research [7, 18], with a 30% difference on a 100 mm-VAS scale, or 13-mm to 22-mm difference, as clinically meaningful [19, 20] [25]. Assuming a standard deviation of 26 mm on the 100-mm VAS scale [7] based on the literature, a total of 96 participants will provide us with an 80% power, using a p-value of 0.05, to detect a 15-mm difference among women presenting for abortion. The enrollment of 96 women is estimated based on a sample size for a t-test. This sample size is adjusted based on the ARE (asymptotic relative efficiency) of the Mann-Whitney U test statistic. The ARE is based on distribution, which is unknown here. Since the ARE for the Mann-Whitney is never less than 0.864, the sample size from the t-test above will be divided by this value. This creates a sample size of 111 women. To account for a potential 20% loss to follow up, the target enrollment goal will be increased to 133 total women for participation in this study. Therefore we determined that 133 women would need to be enrolled.

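### Side effects are compared between arms only by chi-square test; risk differences with confidence intervals would serve the safety aim better at about 66 women per arm

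*Combined protocol and SAP*

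**What the plan says.** Section 1.1.2 lists as a secondary aim: "To evaluate safety of gabapentin in this setting (monitor side effects or adverse events of gabapentin in this setting". The hypothesis in the same section is that gabapentin will "reduce post-operative pain and consumption of pain medication with few adverse effects". Table 1 in section 1.3.2 lists side effects as a secondary outcome. On collection, section 1.3.1 says: "Side effects will be assessed using a checklist prior to discharge", and adds a second assessment at the day-1 contact.

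For analysis, section 1.3.10 gives one rule for all secondary outcomes: "Chi-square and T-tests will be used to evaluate secondary outcomes for categorical and continuous variables, respectively". It specifies no risk difference, confidence interval, margin or target rate for side effects.

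The sample size was set on pain alone. Section 1.3.11 says: "This number was determined to give us sufficient power to detect a 15-mm difference on the 100-mm VAS".

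Section 1.3.7 adds monitoring during the trial. A co-investigator reviews adverse events and periodically compares side effects with what routine care would lead one to expect, and allocation may be revealed if risk is suspected. A data monitoring committee reviews safety data and may set its own stopping rules.

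**The concern.** A chi-square test asks whether the two arms differ. The safety aim asks how much extra dizziness, somnolence and so on a woman might have after taking the drug. In a small trial the two questions come apart: a non-significant p-value is compatible with no excess and with a substantial one, and by itself does not tell the reader which sizes have been ruled out.

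At stake is how the trial can describe tolerability. The protocol presents gabapentin as a low-cost, well-tolerated adjunct for women who go home the same day. If the report gives only p-values for side effects, a true doubling of a common one could easily appear as a non-significant line in a table, with nothing beside it to show the excess still compatible with the data.

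**Working it through.** **The plan's own figure.** Inputs from section 1.3.11: difference 15 mm, SD 26 mm, power 80%, alpha 0.05 (taken as two-sided).

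- Per arm: 2 × (1.96 + 0.84)² × 26² / 15² = 47.2, rounded up to 48, so 96 in total. This matches.
- 96 / 0.864 = 111.1, and 111 × 1.2 = 133.2. This matches the 133.
- No side-effect rate enters. Two arms with "computer-generated random numbers (randomization.com) in variable blocks of 4 and 6" suggest 1:1 allocation, so 67 and 66 women.

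**Power for side effects.** Rates come from the two adverse-reaction tables in section 2. Power is the summed binomial probability of all outcomes at 67 vs 66 in which the test rejects at two-sided 0.05 with more events on gabapentin. Each item is treated as yes/no.

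| Item (gabapentin vs placebo) | Chi-square, uncorrected | With continuity correction |
|---|---|---|
| Epilepsy: dizziness 17% vs 7% | 43% | 31% |
| Epilepsy: somnolence 19% vs 9% | 39% | 28% |
| Epilepsy: ataxia 13% vs 6% | 27% | 17% |
| Epilepsy: fatigue 11% vs 5% | 23% | 14% |
| Postherpetic neuralgia: dizziness 28% vs 8% | 87% | 82% |
| Postherpetic neuralgia: somnolence 21% vs 5% | 82% | 72% |

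The normal approximation agrees. For epilepsy dizziness at 66 per arm, the mean rate is 0.12. The null standard error is √(2 × 0.12 × 0.88 / 66) = 0.0566. The alternative standard error is √(0.17 × 0.83 / 66 + 0.07 × 0.93 / 66) = 0.0559. Then (0.10 − 1.96 × 0.0566) / 0.0559 = −0.19, which gives 42% power. Reaching 80% would take about 165 women per arm for that contrast and 320 for fatigue.

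At 53 per arm (20% missing, relevant to the day-1 contact), uncorrected power is 35% and 31% for epilepsy dizziness and somnolence, and 79% and 72% for the postherpetic neuralgia contrasts.

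**What an interval adds.** Take 12/67 vs 5/66 with dizziness.

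- Chi-square: 133 × (12 × 61 − 5 × 55)² / (67 × 66 × 17 × 116) = 3.19, below 3.84, so not significant.
- Risk difference: 17.9% − 7.6% = 10.3 points.
- Wilson limits: 10.5% to 28.7% and 3.3% to 16.5%.
- Newcombe lower limit: 10.3 − √((17.9 − 10.5)² + (16.5 − 7.6)²) = −1.3.
- Newcombe upper limit: 10.3 + √((28.7 − 17.9)² + (7.6 − 3.3)²) = +22.0 (from unrounded limits).

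The p-value says no significant difference. The interval says that an excess of up to 22 points has not been excluded.

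**If the arms turn out equal.** The 95% half-width, 1.96 × √(2p(1 − p) / 66), is 7.4 points at 5%, 8.7 at 7% and 9.8 at 9%. Equal observed rates would just exclude the 10-point epilepsy excesses in dizziness (placebo 7%) and somnolence (placebo 9%). They would not exclude the 6-point excess in fatigue (placebo 5%).

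**Sparse items.** At a rate of 5% in both arms the expected count is 66 × 0.05 = 3.3 per arm, below the usual 5 for the chi-square approximation.

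**A discrepancy in the inputs.** The narrative in section 2 gives 7% dizziness and 6% ataxia for gabapentin in the epilepsy trials. The table in the same section shows those as the placebo figures, with 17% and 13% for gabapentin. The working uses the table; the two places must be reconciled.

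**The case against.** **The plan never equates non-significance with safety.** A reader might infer that it will declare gabapentin safe if p exceeds 0.05. No section says so. The wording on adverse effects is part of a hypothesis and carries no margin or decision rule; it can be read as a statement about low frequency, which counts per arm would address. This stands. What remains is that no other between-arm analysis is specified.

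**Safety does not rest on chi-square alone.** A reader might also infer that the test is the whole safety assessment. Section 1.3.7 shows otherwise, and this stands too. But both arrangements there are monitoring: they can stop or modify the trial, and they yield no estimate of excess risk.

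**The epilepsy table is the less favourable one.** For the postherpetic neuralgia contrasts in dizziness and somnolence, power is good. This stands, and a null result would carry some evidence against excesses that large.

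**The rates come from repeated dosing.** The protocol says it does not expect the listed effects after a single dose. That is fair, and the table rates are only stand-ins. If single-dose excesses are smaller, however, power at similar background rates is lower still, and an interval becomes more useful.

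**The misses are per item.** It would be too strong to say that the trial would usually show no significant side effect at all. If the epilepsy excesses in dizziness and somnolence were both real and independent, both would be missed with probability 0.567 × 0.614 = 35%. Positive correlation would raise this, to at most 57%.

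**Low power for secondary safety outcomes is normal.** True. The remedy is therefore a better summary of the same data, not a larger trial.

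**Conclusion.** The point holds as an inexpensive improvement to the analysis; the primary comparison is unaffected. Chi-square is the only planned between-arm analysis of side effects. Its power per item is roughly 23% to 43% for excesses of the size in the epilepsy table, and 82% to 87% for the larger postherpetic neuralgia contrasts in dizziness and somnolence. In neither case does the p-value alone tell the reader how large an excess has been excluded, and for items at about 5% or less the chi-square approximation is itself doubtful.

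This rests on 1:1 allocation, a two-sided 0.05 level without multiplicity adjustment, yes/no checklist items (the checklist is not in the text available) and repeated-dose rates standing in for unknown single-dose rates. The documents do not support the stronger conclusion that the plan treats a non-significant test as proof of safety.

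**What to change.** In section 1.3.10, give side effects and adverse events their own sentences:

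- For each checklist item, and for any side effect, report the count and percentage per arm and the risk difference with a 95% confidence interval (for example Newcombe).
- If p-values are still wanted, use an exact test where counts are sparse.
- Base any statement on tolerability on the upper limit of the interval, in the form that an excess above a given number of points is excluded, and not on a non-significant difference.

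A line in section 1.3.11 noting that the sample was sized for pain and not for side effects would help the reader.

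The cost is a few sentences, with no new data, women or visits. The downside is a more cautious safety conclusion: intervals will be roughly 15 to 25 points wide for common effects.

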1.3.2 Criteria for the selection of subjects

Location:

This study will take place at Atlanta Women's Center (AWC), a free-standing abortion clinic in metro-Atlanta that offers abortion services to women up to 23 weeks 6 days gestation.

This clinic operates 4 days per week (Wednesday through Sunday) with a clinical volume of 15 to 45 abortions per day. As abortion services are limited in the southeastern region of the United States, women often travel from other states, including Tennessee, Alabama, Florida,

Mississippi, North Carolina and South Carolina to receive care at this clinic. Approximately 4800 women are seen annually at AWC, with 720 women having abortions under local anesthesia and 3740 women receiving deep sedation anesthesia. Approximately 3320 women are 6-12 weeks GA, 800 women are 13-18 weeks and 340 women are over 18 weeks. Based on the patient volume, we do not anticipate any difficulty in recruiting patients to complete this study within the timeline presented. Misoprostol for cervical preparation is given prior to cases at 10 to 14 weeks per provider preference. Local anesthesia is offered as an option up to 16 weeks, however most cases performed with local anesthesia are less than 14 weeks, with the later gestational ages performed with deep sedation.

AWC, where [name] is the medical director and the study will be conducted, has documented success in participating in and recruiting for several industry sponsored and investigator initiated research studies: a randomized trial of levonorgestrel compared to

Table 1: Outcome measures and covariates	
Primary outcome	
Pain score validated on a 100mm VAS scale measured at time of start of uterine evacuation
Secondary outcomes:	
Pain on VAS scale: preoperatively, completion of procedure (removal of speculum), 10 and 30 min following procedure in the recovery room, at time of dischargeMedication use: pain and nausea medication used during and after procedureNausea/vomiting: pre op and post op nausea per VAS and episodes of vomitingAnxiety: preoperative state anxiety inventorySide effectsPostop assessment via phone on POD#1: pain, nausea, vomiting, and overall clinic experience

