1.3.6 Follow-up procedure

On the day following the procedure (approximately 24 hours after the abortion), study staff will contact the participant to complete the follow-up questions. The participant will be contacted via email, text communication and telephone. Upon completion of the questions, an additional \$20 will be added to the original gift card.

Withdrawals, losses, and deviations:

Randomization to the study method will occur after completion of all intake forms and consent, immediately before the pill is to be taken, thus reducing the possibility of withdrawal after randomization. Any significant medical history will be reviewed prior to enrollment with a clinician at the clinic to ensure study eligibility. Primary outcome measures and most secondary outcome measures will be assessed immediately before, during or after the abortion procedure, thus any loss to follow-up will be limited to those who consent to, but change their mind while waiting for their procedure. Based on current clinical practice at this clinic, withdrawal after consent is extremely rare. Our secondary outcomes assessed post-operatively after discharge will be collected via telephone. We will maximize completion of these assessments through the following steps: participants will be told beforehand about the telephone contact following the procedure, a cellular telephone number will be collected and tested at the clinic, a secondary phone number and email will be collected as a backup, participants will be given a contact number for the study coordinator should they have any challenges with receiving phone calls, and participants will receive an additional \$20 sent to their gift-card following the completion of their phone assessment. Subjects will be considered lost-to-follow-up if they have not responded to the follow up survey within 48 hours after their procedure. As we anticipate some loss to follow-up for our secondary outcome on post-operative day 1, we have adjusted our study enrollment to provide some accommodation for 20% loss to follow-up.

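### The ordered 5-point satisfaction item has no test suited to ordered categories; a 2 x 5 chi-square could cost roughly 20 points of power, a t-test far less

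*Combined protocol and SAP*

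**What the plan says.** Section 1.3.1 includes, in the post-operative day 1 contact described under secondary outcomes, "general satisfaction with the procedure (on a 5-point scale". Table 1, in section 1.3.2, lists the day-1 telephone assessment as "pain, nausea, vomiting, and overall clinic experience", with no scale for the last item, which appears to be the same one.

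Section 1.3.10 covers all secondary outcomes in one sentence: "Chi-square and T-tests will be used to evaluate secondary outcomes for categorical and continuous variables, respectively". For the primary outcome it names two tests: "pain score on 100-mm point VAS) using T-tests and Mann-Whitney U test". Mann-Whitney is not assigned to any secondary outcome, and no trend or ordinal method appears.

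On day-1 attrition, section 1.3.6 says "we have adjusted our study enrollment to provide some accommodation for 20% loss to follow-up". No section gives an expected distribution, effect or power for satisfaction.

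**The concern.** A single five-level rating is ordered categorical data. The two-way rule in 1.3.10 has no place for such data, so the analyst must choose between two imperfect fits.

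- **Chi-square.** A Pearson test on a 2 x 5 table has 4 degrees of freedom. Its value does not change if the five labels are shuffled. It spreads its power over every pattern of difference, whereas the natural question is whether gabapentin moves satisfaction up or down.
- **t-test on the scores.** This uses the order and assumes equal spacing. It is usually close to a rank test, but gives up some power when answers pile up at the top of the scale.

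The two routes can differ materially in power on the same data, and the plan does not say which applies. Because the item is collected on day 1, where the plan expects its losses, there is little information to spare.

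**Working it through.** **1. The plan's own figure.** The only power statement concerns VAS pain. Its variance input is "Assuming a standard deviation of 26 mm on the 100-mm VAS scale". For a 15-mm difference at a significance level of 0.05, section 1.3.11 then states that "a total of 96 participants will provide us with an 80% power". Sidedness and allocation ratio are not stated; I assume two-sided and 1:1.

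Per arm: n = 2(1.960 + 0.842)² × SD² / difference² = 2 × 7.849 × 26² / 15² = 47.2, rounded up to 48, so 96 in total. This reproduces. (The exact t-test gives 48.1 per arm, or 79.9% power at 48.) Then 96 / 0.864 = 111 and 111 × 1.2 = 133. None of this concerns satisfaction.

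**2. Numbers available on day 1.** 133 × 0.80 = 106.4, or about 53 per arm. With no loss, there are about 66 per arm.

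**3. Analytic cost of ignoring order.** Take an effect that lies wholly along the ordered direction and find the noncentrality that gives a 1-df test the stated power at two-sided 0.05. Then test the same noncentrality on 4 df, as a 2 x 5 table would.

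| Power on 1 df | Noncentrality | Power on 4 df | Loss (points) |
|---|---|---|---|
| 50% | 3.841 | 30.8% | 19.2 |
| 70% | 6.172 | 48.2% | 21.8 |
| 80% | 7.849 | 59.5% | 20.5 |
| 90% | 10.507 | 74.0% | 16.0 |
| 95% | 12.995 | 83.7% | 11.3 |

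If some categories go unused, the degrees of freedom fall and so does the loss. At 80% reference power it is 80 − 64.5 = 15.5 points on 3 df and 80 − 70.9 = 9.1 on 2 df.

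**4. Simulation.** Each cell has 4,000 simulated trials, so the Monte Carlo standard error of a power figure is at most √(0.25/4000) = 0.8 points. The control distributions and odds ratios are assumptions. Results at 53 per arm and a proportional-odds ratio of 2.5:

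| Control distribution, lowest to highest (%) | Chi-square | Mann-Whitney | t-test | Loss, chi-square | Loss, t-test |
|---|---|---|---|---|---|
| 20/20/20/20/20 | 50.2% | 73.6% | 73.5% | 23.4 | 0.1 |
| 10/20/40/20/10 | 48.6% | 72.2% | 70.8% | 23.6 | 1.4 |
| 5/10/20/35/30 | 47.9% | 71.2% | 67.8% | 23.3 | 3.4 |
| 2/3/10/30/55 | 36.9% | 60.6% | 54.5% | 23.7 | 6.1 |
| 1/1/3/20/75 | 22.8% | 40.8% | 35.3% | 18.0 | 5.5 |

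Losses are measured against Mann-Whitney. Over odds ratios 1.5 to 4 and both 53 and 66 per arm, the chi-square loss runs from about 3 points (flat distribution, 66 per arm, odds ratio 4: 99.2% against 96.0%) to about 24 (2/3/10/30/55, 66 per arm, odds ratio 2.5: 71.9% against 47.7%). The t-test loss stays within about 0 to 8 points.

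**5. Type I error.** With no effect and 53 per arm, the chi-square rejects in 3.5% of trials for 2/3/10/30/55 and 2.1% for 1/1/3/20/75. Sparse cells make it conservative.

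**6. A case that goes the other way.** With 53 per arm, control 5/10/20/35/30 and treated 15/5/10/25/45, so that the treated arm has more answers at both ends, chi-square power is 58.6% against 14.8% for Mann-Whitney.

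**The case against.** The strongest objection is that a reader might infer from 1.3.10 that the plan commits satisfaction to a chi-square and therefore loses about 20 points of power. The documents do not support that. They never class the item as categorical, and comparing mean scores by t-test fits 1.3.10 equally well and costs little. The form and its response labels are not in the available text, and section 1.3.10 allows a statistician to be consulted where needed. This stands: the larger loss is conditional on the categorical reading. It does not remove the gap, because neither named test is designed for ordered categories and the choice between them is left open.

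Nor is 20 points a fixed property of the design. It needs all five categories in use, a consistent shift, and an ordered test with roughly 50 to 85% power. This also stands, so the size is given as a range.

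Three further inferences are tempting and do not hold:

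- *A significant chi-square would hide the direction.* The p-value alone carries none, but the percentages by arm and category would show it.
- *Sparse cells would produce false positives.* In the cases simulated, the error rate fell below 5%.
- *Satisfaction is a key outcome of the trial.* It is in none of the aims in section 1.1.2. The remark in section 1.1.1 about a woman's experience of abortion is tied to nausea, vomiting and anxiety. A null result on this item would be weak evidence under any test, since the trial is powered only for intraoperative pain.

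**Conclusion.** The point holds in a conditional form. What the documents establish is that the item has five levels, that secondary outcomes are offered only chi-square or t-test, and that no ordered-category method is named for them.

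The cost depends on a choice the plan leaves open: roughly 20 points of power, with a range of about 3 to 24, if the item is tested as a 2 x 5 chi-square against a consistent directional shift; about 0 to 8 points if it is t-tested. Both ranges rest on assumed distributions and proportional-odds effects, two-sided 0.05, 1:1 allocation, and 53 to 66 women per arm.

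This is a cheap improvement of low priority. The primary outcome and the sample size are not affected.

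**What to change.** Add to section 1.3.10:

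> The 5-point satisfaction score will be compared between arms with the tie-corrected Mann-Whitney U test, with the effect given as a proportional-odds ratio and 95% CI. Chi-square is kept for unordered and yes/no outcomes, with Fisher's exact test where expected counts are small.

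Reporting the count in each category by arm alongside would let a reader see any difference that is not a simple shift. It would also help to use one name for the item in section 1.3.1 and Table 1.

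The cost is one sentence, using a test the plan already applies to the primary outcome; it needs no new data, participants or staff. The downside is less power against a non-directional difference, as step 6 of the working shows. The change should be made before the assignments are revealed for analysis.
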